### **3.3.1. Main diagnosis for trial entry**

The trial will be performed in healthy male subjects.

### **3.3.2. Inclusion criteria**

Subjects will only be included in the trial if they meet the following criteria:

1. Healthy male subjects according to the assessment of the investigator, as based on a complete medical history, including a medical examination, vital signs (BP, PR), 12-lead ECG, and clinical laboratory tests
2. Japanese ethnicity, according to the following criteria:
  - born in Japan, have lived outside of Japan <10 years, and have parents and grandparents who are Japanese
3. Age of 20 to 45 years (inclusive) at screening
4. BMI of 18.5 to 25.0 kg/m^2 (inclusive) at screening
5. Signed and dated written informed consent prior to admission to the trial, in accordance with Good Clinical Practice (GCP) and local legislation
6. Subjects who agree to minimize the risk of making their partner pregnant by fulfilling any of the following criteria starting from the first administration of trial medication until 90 days after last administration of trial medication
  - Use of adequate contraception, any of the following methods plus condom: intrauterine device, combined oral contraceptives that started at least 2 months prior to the first drug administration.
  - Vasectomized (vasectomy at least 1 year prior to enrolment)
  - Surgical sterilization (including bilateral tubal occlusion, hysterectomy or bilateral oophorectomy) of the subject's female partner
7. Subjects genotyped as UGT2B17 poor metabolizers, i.e. carrying allele of UGT2B17 gene (\*2/\*2) (DDI and MD part only)

### **3.3.3. Exclusion criteria**

Subjects will not be allowed to participate, if any of the following general criteria apply:

1. Any finding in the medical examination (including BP, PR or ECG) deviating from normal and assessed as clinically relevant by the investigator
2. Repeated measurement of systolic blood pressure outside the range of 90 to 140 mmHg, diastolic blood pressure outside the range of 40 to 90 mmHg, or pulse rate outside the range of 40 to 99 bpm
3. Any laboratory value outside the reference range that the investigator considers to be of clinical relevance

Proprietary confidential information © 2021 Boehringer Ingelheim International GmbH or one or more of its affiliated companies

4. Any evidence of a concomitant disease assessed as clinically relevant by the investigator
5. Gastrointestinal, hepatic, renal, respiratory, cardiovascular, metabolic, immunological or hormonal disorders
6. Cholecystectomy or other surgery of the gastrointestinal tract that could interfere with the pharmacokinetics of the trial medication (except appendectomy or simple hernia repair)
7. Diseases of the central nervous system (including but not limited to any kind of seizures or stroke), and other relevant neurological or psychiatric disorders
8. History of relevant orthostatic hypotension, fainting spells, or blackouts
9. Chronic or relevant acute infections (Subjects who were positives to Hepatitis B surface antigen, Hepatitis B surface antibody, Hepatitis B core antibody, Hepatitis C antibodies, HIV-1 and HIV-2 antigen and/or antibody, T-SPOT and Syphilis test)
10. History of relevant allergy or hypersensitivity (including allergy to the trial medication or its excipients)
11. Use of drugs within 30 days of planned administration of trial medication that might reasonably influence the results of the trial (including drugs that cause QT/QTc interval prolongation)
12. Intake of an investigational drug in another clinical trial within 3 months (4 months for new active ingredients) of planned administration of investigational drug in the current trial, or concurrent participation in another clinical trial in which investigational drug is administered
13. Smoker (more than 10 cigarettes or 3 cigars or 3 pipes per day)
14. Inability to refrain from smoking on specified trial days
15. Alcohol abuse (consumption of more than 30 g per day for males)
16. Drug abuse or positive drug screening
17. Blood donation of more than 400 mL within 12 weeks or 200 mL within 30 days or plasma donation within 2 weeks prior to administration or intended blood donation during the trial
18. Intention to perform excessive physical activities within one week prior to the administration of trial medication or during the trial
19. Inability to comply with the dietary regimen of the trial site
20. A marked baseline prolongation of QT/QTc interval (such as QTc intervals that are repeatedly greater than 450 ms in males) or any other relevant ECG finding at screening
21. A history of additional risk factors for *Torsade de Pointes* (such as heart failure, hypokalaemia, or family history of Long QT Syndrome)
22. Subject is assessed as unsuitable for inclusion by the investigator, for instance, because the subject is not considered able to understand and comply with trial requirements, or has a condition that would not allow safe participation in the trial

### 23. History of disease that affects the present situation

In addition, the following trial-specific exclusion criteria apply:

24. Current or history of relevant kidney, urinary tract diseases or abnormalities (e.g. nephrolithiasis, hydronephrosis, acute or chronic nephritis, renal injury, renal failure)
25. Estimated glomerular filtration rate according to Chronic Kidney Disease Epidemiology Collaboration (CKD-EPI\*) formula < 80 mL/min at screening
26. Within 10 days prior to administration of trial medication, use of any drug that could reasonably inhibit platelet aggregation or coagulation (e.g. acetylsalicylic acid)
27. History of drug induced liver injury
28. Liver enzymes (ALT, AST, Gamma-Glutamyl Transferase [GGT]) above upper limit of normal at the screening examination
29. Known relevant immunodeficiency, as judged by the investigator
30. History and/or presence of tuberculosis; positive result for interferon gamma release assay (IGRA) (i.e. T-SPOT), or history of pneumococcal infection
31. Axillary temperature of more than 37.7°C on Day -1
32. Subjects who have received live or live-attenuated vaccine in the 4 weeks prior to dosing
33. C-reactive protein above upper limit of laboratory reference range at screening

\* Estimated glomerular filtration rate by Japanese CKD-EPI formula

For trial restrictions, refer to Section [4.2.2](#).

#### 3.3.4. Withdrawal of subjects from treatment or assessments

Subjects may discontinue trial treatment or withdraw consent to trial participation as a whole ('withdrawal of consent') with very different implications; please see sections [3.3.4.1](#) and [3.3.4.2](#) below.

If a subject is removed from or withdraws from the trial prior to the first administration of trial medication, the data of this subject will not be entered in the case report form (CRF) and will not be reported in the clinical trial report (CTR). If a subject is removed from or withdraws from the trial after the first administration of trial medication, this will be documented and the reason for discontinuation must be recorded in the CRF; in addition, the data will be included in the CRF and will be reported in the CTR.

At the time of discontinuation, a complete end of trial examination will be performed, if possible, and the information will be recorded in the CRF. If the discontinuation occurs before the end of the REP (see Section [1.2.3](#)), the discontinued subject should if possible be questioned for AEs and concomitant therapies at or after the end of the REP in order to ensure collection of AEs and concomitant therapies throughout the REP, if not contrary to any consent withdrawal of the subject.

### 3.3.4.1. Discontinuation of trial treatment

An individual subject will discontinue trial treatment if:

1. The subject wants to discontinue trial treatment or trial participation, without the need to justify the decision
2. The subject has repeatedly shown to be non-compliant with important trial procedures and, in the opinion of both, the investigator and sponsor representative, is not willing or able to adhere to the trial requirements in the future
3. The subject needs to take concomitant medication that interferes with the investigational medicinal product or other trial treatment
4. The subject is no longer able to participate in the trial for other medical reasons, such as surgery, adverse events (AE)s, or diseases
5. The subject has an elevation of AST and/or ALT  $\geq 3$ -fold ULN and an elevation of total bilirubin  $\geq 2$ -fold ULN (measured in the same blood sample) and/or needs to be followed up according to the DILI checklist provided in the ISF

In addition to these criteria, the investigator may discontinue subjects at any time based on his or her clinical judgment.

Even if the trial treatment is discontinued, the subject remains in the trial and, given his agreement, will undergo the procedures for early treatment discontinuation and follow up as outlined in the [Flow Chart](#) and section [6.2.3](#).

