Period 2/Treatment T (BI 1323495 + itraconazole) 	3	-3	-72:00	09:00	Ambulatory visit, itraconazole administration	x B,2,3			x			x 
		-2	-48:00	09:00	Ambulatory visit, itraconazole administration							x 
		-1	-24:00	09:00	Ambulatory visit, itraconazole administration 	x C,2,3		x 				x 
			-12:00	21:00	Admission to trial site 							
	1 		-2:00	07:00			x 		x 	x 	x 	x 
			-1:00	08:00	Itraconazole administration			x 				
			0:00	09:00	BI 1323495 administration							
			0:20	09:20			x					
			0:40	09:40			x					
			1:00	10:00			x					
			1:30	10:30			x					
			2:00	11:00	240 mL fluid intake		x					
			3:00	12:00			x					
			4:00	13:00	240 mL fluid intake, thereafter lunch 		x		x	x	x	
			5:00	14:00			x					
			6:00	15:00			x					
			7:00	16:00	Snack (voluntary) 		x					
			8:00	17:00			x					
			9:00	18:00			x					
			10:00	19:00	Dinner 		x					
			12:00	21:00			x					x
	2		23:00	08:00	Itraconazole administration	x B,2						x
			24:00	09:00	Breakfast (voluntary) 		x		x	x	x	
			28:00	13:00	Lunch (voluntary)							
			31:00	16:00	Snack (voluntary)							x
			34:00	19:00	Discharge from trial site		x					x
	3		47:00	08:00	Ambulatory visit, itraconazole administration		x 	x 				x
			71:00	08:00	Ambulatory visit, itraconazole administration	x C,2	x 					x
	4		95:00	08:00	Ambulatory visit, itraconazole administration		x 					x
			119:00	08:00	Ambulatory visit, itraconazole administration	x C,2	x 					x
			143:00	08:00	Ambulatory visit, itraconazole administration		x 	x 				x
			167:00	08:00	Ambulatory visit	x B	x	x				x
EOT	4	16 to 23			End of trial (EOT) examination 	x A			x	x	x	x

Clock time should be adjusted based on actual administration time

1. Subject must be informed and written informed consent obtained prior to starting any screening procedures. Screening procedures include medical examination, check of vital signs, ECG(12-lead ECG), chest x-ray, safety laboratory (including drug screening), pharmacogenetic analysis for UGT2B17 genotype, demographics (including determination

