Proprietary confidential information © 2021 Boehringer Ingelheim International GmbH or one or more of its affiliated companies

of body height and weight, smoking status and alcohol history), relevant medical history, concomitant therapy and review of inclusion/exclusion criteria.

2. The time is approximate; the procedure is to be performed and completed within the 3 h prior to drug administration.
3. Urine drug screening and alcohol breath test
4. If several actions are indicated at the same time, the intake of meals will be the last action.
5. Letters A, B and C define different sets of safety laboratory examinations (for details refer to Section [5.2.3](#))
6. At the end of trial visit the EOT examination includes medical examination, vital signs, ECG, safety laboratory, recording of AEs and concomitant therapies.
7. AEs and concomitant therapies will be recorded throughout the trial, but will be specifically asked for at the times indicated in the [Flow Chart](#) above.
8. Administration of BI 1323495 in treatment R and T will be separated by at least 11 days.
9. Blood collection takes place at the indicated times. Itraconazole will be administered immediately thereafter.
10. For allowed deviation from the scheduled time please refer to Section [6.1](#).
11. Axillary temperature measurement will be conducted during Day -1.
12. PGx samples will be collected during Day 1.

Proprietary confidential information © 2021 Boehringer Ingelheim International GmbH or one or more of its affiliated companies

MD part (30 mg bid)

Visit	Day	Planned time (relative to first drug administration [h:min])	Approximate clock time of actual day [h:min]	Event and comment	Safety laboratory 		PK blood 	PK urine 	PD blood (NE activity)	12-lead ECG 	Medical examination	Vital signs 	Questioning for AEs and concomitant therapy 
1	-28 to -8			Screening (SCR)  including pharmacogenomics test UGT2B17	x A					x	x	x	
2 	1 	-1	-16:00	17:00 Admission to trial site	x B, 6, 10, 11							x	
			-01:00	08:00 Allocation to treatment 	x C,12	x 	x 	x 	x 	x 	x 	x 	
			-00:30	08:30 breakfast									
			00:00 09:00	First drug administration 			▲						
			00:20	09:20		x	—						
			00:40	09:40		x	—						

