The healthy subject population of this study, as defined by the in- and exclusion criteria, is not affected by any clinically relevant concomitant diseases that might put them at an increased risk of experiencing a severe clinical course of COVID-19 in case of SARS-CoV-2 infection.

Based on these considerations, the benefit/risk assessment for the administration of BI 1323495 to healthy subjects remains unaltered also in face of the COVID-19 pandemic.

*Risk mitigation:*

Ensure that the general measures implemented by the government to control the spread of COVID-19 in the Japanese population are adhered to. COVID-19 infection testing such as PCR test will be conducted before hospitalization.

Itraconazole

In this trial itraconazole will be used in a standard clinical dose of 200 mg once daily for 10 days. Multiple dosing of 200 mg itraconazole up to 15 days was of acceptable tolerability in healthy subjects ([c02336088](#), [c03355329](#), [c08928447](#), [R17-3742](#)). Addition to this, BI 1323495 will not have potential to be CYP3A4 inhibitor.

For a detailed description of the potential risks of itraconazole treatment, please refer to the package insert for ITRIZOLE® Oral Solution 1% ([R20-1269](#)).

Proprietary confidential information © 2021 Boehringer Ingelheim International GmbH or one or more of its affiliated companies

In order to address the risk of hepatotoxicity, only subjects with normal liver enzyme values will be included into the trial. Safety laboratory parameters will be monitored closely.

An individual subject will discontinue the treatment if the subject shows an elevation of AST and/or ALT  $\geq 3$ -fold ULN combined with an elevation of total bilirubin  $\geq 2$ -fold ULN (measured in the same blood sample, see Section [3.3.4.1](#)).

Further, most of the reported cases of serious hepatotoxicity during itraconazole treatment occurred in patients that suffered from concomitant liver diseases, had other significant diseases, or took concomitant hepatotoxic drugs. Subjects with liver diseases or a medical history of drug-induced liver failure are excluded from trial participation.

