**Table 4.1.4: 3 Dosage and treatment schedule in the DDI part**

Treatment period	Treatment	Substance	Formulation	Unit strength	Dosage	Total dose
1	R (Reference)	BI 1323495	Tablet, film-coated	10 mg	1 tablet as single dose (Day 1)	10 mg
2	T (Test)	BI 1323495	Tablet, film-coated	10 mg	1 tablet as single dose (Day 1)	10 mg
		Itraconazole	Oral solution	10 mg/mL	20 mL (200 mg) qd for 10 days (Days -3 to 7)	2000 mg

Table 4.1.4: 4 BI 1323495 and placebo treatments, tablets of MD part for PM

Dose group	Substance	Pharmaceutical form	Unit strength	Number of units per administration	Total daily dose of BI 1323495
1	BI 1323495	Tablet, film-coated	10 mg	3 tablets bid*	60 mg
1	Placebo	Tablet, film-coated	--	3 tablets bid*	--
2	BI 1323495	Tablet, film-coated	10 mg 50 mg	1 tablet each qd	60 mg
2	Placebo	Tablet, film-coated	--	1 tablet each qd	60 mg

\*On Day 11, Subjects will receive a single dose in the morning only. On all other trial days, BI 1323495 will be administered bid.

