#### **5.2.3. Safety laboratory parameters**

For the assessment of laboratory parameters, blood and urine samples will be collected by the trial site at the time points indicated in the [Flow Chart](#) after the subjects have fasted for at least 10 h, except 4 h post dosing on Day 1 of SRD part and screening. For retests, at the discretion of the investigator or designee, overnight fasting is not required. The parameters that will be determined are listed in Tables [5.2.3: 1](#) and [5.2.3: 2](#). Reference ranges will be provided in the ISF, Section [10](#).

Manual differential white blood cell count or urine sediment examinations will only be performed if there is an abnormality in the automatic blood cell count or in the urinalysis, respectively.

Table 5.2.3: 1 Routine laboratory tests

Functional lab group	BI test name [comment/abbreviation]	A 	B 	C 	D 
Haematology	Haematocrit	X	X	--	X
	Haemoglobin	X	X	--	X
	Red Blood Cell Count/Erythrocytes	X	X	--	X
	White Blood Cells/Leucocytes	X	X	--	X
	Platelet Count/Thrombocytes (quant)	X	X	--	X
Automatic WBC relative	Neutrophils/Leukocytes; Eosinophils/Leukocytes; Basophils/ Leukocytes; Monocytes/Leukocytes; Lymphocytes/Leukocytes	X	X	--	X
Automatic WBC differential	Neutrophil, absol.; Eosinophils, absol.; Basophils, absol.; Monocytes, absol.; Lymphocytes, absol.	X	X	--	X
Manual differential WBC (if automatic differential WBC is abnormal and clinically relevant in the opinion of the investigator)	Neut. Poly (segs; Neutrophils Bands; Eosinophils/Leukocytes; Basophils/ Leukocytes; Monocytes/ Leukocytes; Lymphocytes/Leukocytes;				
Coagulation	Activated Partial Thromboplastin Time	X	--	--	--
	Prothrombin time	X	--	--	--
	INR (International Normalization Ratio)	X	--	--	--
	Fibrinogen	X	X	--	--
Enzymes	AST [Aspartate transaminase] /GOT	X	X	X	--
	ALT [Alanine transaminase] /GPT	X	X	X	--
	Alkaline Phosphatase	X	X	X	--
	Gamma-Glutamyl Transferase	X	X	X	--
	Creatine Kinase [CK]	X	X	--	--
	Creatine Kinase Isoenzyme MB [only if CK is elevated and clinically relevant in the opinion of the investigator]	X	X	--	--
Hormones	Thyroid Stimulating Hormone	X	--	--	--
Substrates	Glucose (Plasma)	X	X	--	--
	Creatinine	X	X	--	--
	GFR/ CKD-EPI	X	X	--	--
	Bilirubin, Total	X	X	--	--
	Bilirubin, Direct	X	X	--	--
	Protein, Total	X	X	--	--
	C-Reactive Protein (Quant)	X	X	--	--
	Cholesterol, total	X	--	--	--
Electrolytes	Triglyceride	X	--	--	--
	Sodium	X	X	--	--
	Potassium	X	X	--	--

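### In DDI Period 2, lab set C measures AST and ALT but not total bilirubin, so a set C sample at 3 to <10 times ULN cannot be judged against the same-sample liver stopping rule

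*Protocol*

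**What the plan says.** - **Stopping rule.** Protocol Section 3.3.4.1, item 5, makes discontinuation mandatory when AST and/or ALT is at least 3 times ULN and total bilirubin at least 2 times ULN, "measured in the same blood sample) and/or needs to be followed up according to the DILI checklist provided in the ISF".
- **Purpose of the rule.** Section 1.4.2 repeats it under itraconazole ("An individual subject will discontinue the treatment if the subject shows an elevation of AST and/or ALT"...) as part of the answer to hepatotoxicity, next to the assurance "Safety laboratory parameters will be monitored closely".
- **AESI definition.** Section 5.2.6.1.4 defines hepatic injury by the same combination in one sample, or by ALT and/or AST of at least 10 times ULN alone. Either finding sends the subject to the DILI checklist.
- **Panels.** In Table 5.2.3: 1 the row "Bilirubin, Total" is marked for sets A and B and not for C or D. Set C consists of AST, ALT, alkaline phosphatase and GGT.
- **Schedule.** The DDI Flow Chart for Period 2 places set C at -24, 71 and 119 h relative to BI 1323495 (Days -1, 4 and 6), and set B at -72, 23 and 167 h.
- **Dosing.** Table 4.1.4: 3 gives itraconazole as "20 mL (200 mg) qd for 10 days (Days -3 to 7".

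**The concern.** Set C is purely a liver-enzyme panel, used only a few days apart while itraconazole is being given. It omits the one further analyte that the liver stopping rule needs. Below 3 times ULN bilirubin is irrelevant, and at 10 times ULN or more the DILI limb applies without it. In the band between, bilirubin alone decides whether treatment must stop, and there a set C sample turns a mandatory rule into a matter of investigator discretion.

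The same missing value decides whether the event is an AESI. That status brings reporting to the sponsor within 24 h (Protocol Sections 5.2.6.1.4 and 5.2.6.2.2) and a place in the overall AE summary (SAP Section 7.8.1). The subjects are healthy volunteers with no therapeutic benefit, so the safety rules should work as written.

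**Working it through.** The plan gives no figure to reproduce. The check sets the panel contents against the Period 2 schedule.

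**Inputs** (hours relative to BI 1323495, from the DDI Flow Chart; days inferred from the hours):
- Itraconazole doses: -72, -48, -24, -1, 23, 47, 71, 95, 119, 143, which is 10 doses and agrees with Table 4.1.4: 3.
- Panels with bilirubin (set B): -72, 23, 167.
- Panels without bilirubin (set C): -24, 71, 119.
- Flow Chart footnote 2 applies to the set C samples: "the procedure is to be performed and completed within the 3 h prior to drug administration". The sample therefore precedes that day's itraconazole dose.

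**What a set C sample can decide:**
- AST and ALT both <3 times ULN: rule not met.
- AST or ALT ≥10 times ULN: DILI checklist limb met, so item 5 applies.
- AST or ALT ≥3 times ULN, neither ≥10 times: undetermined, because the bilirubin term is missing.

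**Coverage:**
- All Period 2 panels: 3 of 6 lack bilirubin. With 14 subjects, that is 14 × 3 = 42 of 14 × 6 = 84 planned subject-samples.
- Panels after the first itraconazole dose and before the last (-24, 23, 71, 119 h): 3 of 4 lack bilirubin.
- Longest interval without scheduled bilirubin: 167 - 23 = 144 h. The doses at 23, 47, 71, 95, 119 and 143 h fall in it, 6 of 10. The sample that closes the interval follows the last dose.

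**Wait from each set C sample to the next scheduled bilirubin:**

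| Set C sample | Next scheduled bilirubin | Wait | Itraconazole doses in the wait, with same-day dose | Without same-day dose |
|---|---|---|---|---|
| -24 h (Day -1) | 23 h | 23 + 24 = 47 h | 2 (-24, -1) | 1 |
| 71 h (Day 4) | 167 h | 167 - 71 = 96 h | 4 (71, 95, 119, 143) | 3 |
| 119 h (Day 6) | 167 h | 167 - 119 = 48 h | 2 (119, 143) | 1 |

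The last column applies if the result arrives only after that day's dose. For the Day -1 sample, the BI 1323495 dose at 0 h also falls in the wait.

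**How often the case might arise.** The documents give no rate. Let *p* be an assumed per-subject probability of a set C value at ≥3 and <10 times ULN. The chance of at least one such subject among 14 is 1 - (1 - *p*)^14:
- *p* = 0.5%: 6.8%
- *p* = 1%: 13.1%
- *p* = 2%: 24.6%
- *p* = 5%: 51.2%

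These figures show only how the chance depends on the assumption.

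**The case against.** Item 5 applies to a subject, not to each scheduled sample. A retest that includes AST, ALT and bilirubin is itself one blood sample and could meet the rule. Nothing forbids adding bilirubin to the set C sample either.

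A retest is also easy to arrange. Subjects attend daily for itraconazole ("Ambulatory visit, itraconazole administration") or are in the unit, so one is possible within about 24 h. The waits in the table run to the next scheduled bilirubin, not to the earliest possible one.

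Other provisions help:
- Section 6.2.3 says that abnormal values judged clinically relevant will be monitored with suitable tests.
- Section 3.3.4.1 lists adverse events among the medical reasons for stopping (item 4), and allows the investigator to stop a subject on clinical judgement.
- Exclusion criterion 28 removes subjects with raised ALT, AST or GGT at screening.
- Section 1.2.1 reports no relevant laboratory changes in trial 1405-0009, in which 14 extensive metabolizers were treated with the same combination.

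A short enzyme panel between full panels, with further work-up on a signal, is a legitimate design.

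All of this lowers the likely frequency and the practical delay. None of it makes a bilirubin test mandatory when an asymptomatic subject has a raised transaminase on set C. Section 6.2.3 depends on a judgement of relevance and names no analyte or threshold. On retests Section 5.2.3 says only: "For retests, at the discretion of the investigator or designee, overnight fasting is not required". Section 5.2.6.1.4 explicitly calls for an unscheduled test only when there are clinical symptoms. It sends subjects to the DILI checklist once an alert criterion is met, which in this band requires the missing bilirubin.

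**Conclusion.** The concern holds. The panel and the stopping rule do not match: on Days -1, 4 and 6 of DDI Period 2, the scheduled laboratory set cannot complete the rule for AST or ALT from 3 to below 10 times ULN. The omission covers half of the Period 2 panels and three of the four taken between the first and last itraconazole doses. Only samples in that band are affected, and they should be few.

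The conclusion rests on the protocol text. The DILI checklist and the laboratory manual are not among the documents, and a reflex bilirubin test in either would close the gap. The primary PK endpoints, the DDI model and the sample size are untouched. This should be fixed because it weakens a stated safety control and is cheap to correct.

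**What to change.** Either change closes the gap and raises the panels between the first and last itraconazole doses that can be classified from 1 of 4 to 4 of 4.

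1. **Reflex test.** State in Protocol Section 5.2.3 that total bilirubin is to be measured on the same sample whenever AST or ALT is at least 3 times ULN. This costs one sentence and an occasional assay.
2. **Routine test.** Add total bilirubin to set C in Table 5.2.3: 1. This costs one analyte on blood already drawn at three visits, with no new visit.

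The routine option has a side effect. SAP Section 6.7 takes baseline as the last value before BI 1323495, so the Period 2 bilirubin baseline would move from Day -3, before itraconazole, to Day -1, after two doses (-72 and -48 h). The AST and ALT baseline is already on Day -1. The stopping rule is ULN-based and does not depend on baseline. The reflex option largely avoids the shift and is the lighter change.
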